2. The clinic psychiatrist will ask patients that they feel are clinically appropriate to see if he or she would agree to be contacted about this research protocol.
3. If the patient agrees, then a study psychiatrist or psychologist would meet with the patient to describe the study and ask if the patient would be interested in participating.
4. If the patient is interested in the study and appears to meet general eligibility criteria, the patient would be evaluated for capacity to give informed consent, and if they have adequate capacity, then provide written informed consent.

Control subjects and patients from the community will be approached after they answer advertisements.

How will the study be advertised/publicized?

The study will be publicized to patients with schizophrenia via contact with the Lieber Schizophrenia Research clinic. Non-clinical control participants will be recruited by word of mouth, fliers, through our division's website and Craigslist. Advertisements will be submitted to the IRB prior to initiation of studies.

Do you have ads/recruitment material requiring review at this time?

No

Does this study involve a clinical trial?

Yes

Please provide the NCT Registration Number

NCT01898299

Concurrent Research Studies

Will subjects in this study participate in or be recruited from other studies?

Yes

Describe concurrent research involvement

**#4158 Lieber Schizophrenia Research Clinic (LSRC) Umbrella Protocol
6691: MOSAIC: The Management Of Schizophrenia In Clinical Practice**

Inclusion/Exclusion Criteria

Name the subject group/sub sample

Schizophrenia patients with auditory hallucinations

Create or insert table to describe the inclusion criteria and methods to ascertain them

Criterion	Method of Ascertainment
1. Age between 18-55	Self report
2. SCID primary diagnosis of DSM-IV schizophrenia or schizoaffective disorder	SCID
3. Persistent auditory verbal hallucinations	Auditory Hallucinations Rating Scale mean item score >2 and stable mean score >2 or within 25% of screening score at baseline
4. Right handed	Edinburgh Handedness Questionnaire
5. Stable antipsychotic medication for >4 weeks	Physician evaluation/Psychiatric history
6. Normal hearing	Physician evaluation

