An M.D. who is unaffiliated but familiar with the study will ask potential participants who have been diagnosed with schizophrenia questions about the study procedures and associated risks in order to determine whether the patient understands the study and has the capacity to provide consent.

Study Procedures

Describe the procedures required for this study

Overview

AH + Sample

The treatment portion of this study will follow a double-blind parallel arm design in which patients, raters and investigators will be blinded with respect to condition assignment. All personnel will have undergone HIPAA and CITI training. Following a clinical evaluation to determine eligibility, patients will be assigned to either the active or the sham condition. In the active condition, patients will receive cathodal stimulation to the left temporo-parietal junction and anodal stimulation to the left dorsolateral prefrontal cortex at 2mA X 20 min in each session. In the sham condition, electrodes will be placed over the same regions, but current will be applied under a “sham” approach in which currents are initially ramped up over 30 s as in the active condition, but then immediately ramped down. Prior experience has shown that subjects do not distinguish the active and sham conditions. Patients will participate in two daily sessions of 20 minutes each for 5 consecutive weekdays. Auditory hallucinations as determined by the Auditory Hallucinations Rating Scale (AHRS) and the five dimensions of schizophrenia symptoms assessed in the Positive and Negative Syndrome Scale (PANSS) will be assessed at baseline, immediately following the final treatment, and at 1- and 3-month follow-up timepoints. AHRS will be repeated prior to first treatment session. All subjects will be assessed prior to and following initiation of 5-d treatment period using a neurophysiological battery sensitive to auditory dysfunction in schizophrenia, and neuropsychological tests of auditory and general neurocognitive impairment. The neurophysiological impact of tDCS will be assessed by MRI procedures described below at baseline and immediately following the final treatment. MRI sessions are optional for AVH+ patients.

Comparison Samples

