Additionally, subjects will receive the CGI-I scale prior to each treatment session to evaluate clinical stability. Additionally, **at baseline and after the final treatment**, patients will undergo pure tone audiometry testing for safety screening. If a change in auditory threshold is discovered, the treating physician will inform the patient and discuss whether or not to continue with treatment. Furthermore, if a change is discovered, the patient's hearing will be tested again periodically until either it returns baseline or the clinician determines that the change is permanent.

Post-treatment Assessments

Immediately following completion of last treatment, patients in the AH+ sample will have 1 tube of blood drawn for BDNF levels. Within 1 week following completion of treatment, patients will have repeat of baseline behavioral and ERP methods. Behavioral assessments will also be repeated at 1- and 3-month follow-up timepoints. Response to treatment will be defined as >15% reduction in AHRS score. **After the completion of the 3 month visit, subjects will be offered the opportunity to do one week of optional, open label active treatment using identical procedures to the blinded treatment. Subjects will be seen once after the week of open treatment for a follow-up visit**

Schedule of Events

Please see attached table.

Comparison Samples

Participants in the AH- and non-clinical control samples will take part in a baseline assessment session only. AH- patients will be assessed via the SCID, AHRS, PANSS/SQLS, MATRICS/TMT, and ERP procedure. Non-clinical control participants will be assessed via the SCID-NP procedure.

Genetics Blood draw:

Only AVH+ subjects will be asked to participate in the genetics blood draw.

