In reviewing the literature, we note that there is also evidence that BDNF gene polymorphisms affect response to tDCS (Antal A, Chaieb L, Moliadze V, Monte-Silva K, Poreisz C, Thirugnanasambandam N, Nitsche MA, Shoukier M, Ludwig H, Paulus W. Brain-derived neurotrophic factor (BDNF) gene polymorphisms shape cortical plasticity in humans. *Brain Stimul*. 2010;3:230-7). It has also been demonstrated that individuals with common polymorphisms of the BDNF gene may show differential response to tDCS enhancement of brain plasticity. Thus, for both facilitatory tDCS (24 subjects, 10 heterozygotes) and inhibitory tDCS (19 subjects, 8 heterozygotes), carriers of the Val66Met allele displayed enhanced plasticity. In the present study, we will perform a secondary analysis to evaluate whether Val66 Met carriers show preferential response to tDCS treatment.

You can upload charts or diagrams if any

Criteria for Early Discontinuation

Criteria for Early Discontinuation

Treatment Termination

Study participation for patients in the AH+ sample will be terminated for subjects with a CGI-I worsening of 2 or greater for two consecutive days, or a CGI-S of 6 or 7 at anytime.

Participants in all samples may choose to terminate their involvement at any time.

Blood and other Biological Samples

Please create or insert a table describing the proposed collection of blood or other biological specimens
Blood samples will be drawn for patients in the AH+ sample only. No blood or biological samples will be collected from participants in the AH- or non-clinical control samples.

12 cc at screening will be drawn for blood work-up (Chem 20, Thyroid function) to determine tDCS treatment safety.

30 cc tube of blood will be collected for D-serine and BDNF assessment and genetics (optional).

Assessment Instruments

Create a table or give a brief description of the instruments that will be used for assessment

SCID: 60 min

SCID-NP: 30 min

AHRS: 20 min

PANSS: 30 min

MATRICES battery (without SC): 1 hr

Tone Matching Test: 20 min

SQLS: 15 min

EEG for ERP procedures: 3 hrs

Wong-Baker Faces Pain Rating Scale 1 minute

CGI-S and CGI-I 5 minutes

Brunoni safety scale 5 minutes

Please attach copies, unless standard instruments are used

Off label and investigational use of drugs/devices

Choose from the following that will be applicable to your study

✓ Device

Off label and investigational use of devices

Device #1

Name of the device

BrainStim SYS

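### Read literally, the early-discontinuation rule ends study participation rather than tDCS alone, so primary AHRS data could be lost because a patient worsened

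*Protocol*

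**What the plan says.** The rule is in the Protocol, *Criteria for Early Discontinuation*, under the sub-heading "Treatment Termination". It reads "Study participation for patients in the AH+ sample will be terminated for subjects with a CGI-I worsening of 2 or greater" on two consecutive days, "or a CGI-S of 6 or 7 at anytime".

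The timing of the assessments comes from three places in *Study Procedures*:

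- *Safety*: "subjects will receive the CGI-I scale prior to each treatment session to evaluate clinical stability".
- *Overview, AH+ Sample*: AHRS and PANSS "will be assessed at baseline, immediately following the final treatment, and at 1- and 3-month follow-up timepoints".
- *Post-treatment Assessments*: "Within 1 week following completion of treatment, patients will have repeat of baseline behavioral and ERP methods", with behavioural repeats at 1 and 3 months.

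The full visit plan under *Schedule of Events* is given only as "Please see attached table", and that table is not among the documents.

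The SAP's primary endpoint is percent change across AHRS items, analysed at one week and one month after randomisation. The SAP does not say how a patient without those values is handled.

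**The concern.** Stopping stimulation in a patient who is getting worse is a safety measure, and nobody would object to it. Ending the patient's participation in the study goes further, because it also ends outcome measurement. The trigger is clinical worsening after randomisation, so the missing AHRS values would come from patients selected for doing badly. The SAP's covariates (baseline AHRS and chlorpromazine equivalents) do not capture what happened after randomisation, so they cannot repair this.

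If the rule fires equally often in both arms, the arm difference is little affected. If it fires more often on sham, the poorest sham outcomes disappear and benefit is hidden. If it fires more often on active, harm is hidden.

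**Working it through.** **1. What is terminated?** The sentence says study participation and the sub-heading says treatment. Three features of the text favour the literal reading:

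- For a change in hearing, *Safety* speaks of whether to go on with treatment, so the Protocol can say treatment when it means treatment.
- *Description of subject population* separately allows removal from the study for non-compliance, a change in medical status or an adverse event.
- The sentence after the rule lets participants in every sample end their involvement. Two of the three samples receive no tDCS, so that sentence must concern the study.

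These points do not settle the intent.

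**2. Does the rule act before the primary outcome?** CGI-I is scheduled before each session, and no available text schedules it later. The CGI-I trigger therefore acts within the five treatment days. Both primary time points come afterwards, so under the literal reading a patient stopped this way has neither value. The CGI-S trigger has no time limit and could also act between the two visits, which would cost only the second.

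**3. Is there a provision for such patients?** The post-treatment assessment is tied to the end of treatment, and the later visits are listed without mention of patients who stopped early. No available text keeps them in follow-up.

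**4. How large could the effect be?** The Protocol and SAP give no stop rate, SD or CGI–AHRS correlation, so there is no planned figure to reproduce. What follows is an illustration.

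Inputs:

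- 75 AH+ patients to be enrolled (*Description of Subject Population*, Sample #1). With equal allocation assumed, this is about 37 per arm. The 60 in the same section are completers, and a stopped patient is not a completer, so 60 is the wrong denominator.
- Assumed: CGI change and AHRS change are bivariate normal with correlation ρ of 0.3 to 0.5, and the rule removes the worst fraction q on CGI.

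Shift in the mean of the remaining patients, in SD: ρ × φ(z) / (1 − q), where z cuts off the upper fraction q of a standard normal and φ is its density.

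At ρ = 1:

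- 1 of 37: q = 0.027, φ(z) = 0.0624, shift 0.0624 / 0.973 = 0.064
- 2 of 37: q = 0.054, φ(z) = 0.1097, shift 0.1097 / 0.946 = 0.116
- 3 of 37: q = 0.081, φ(z) = 0.1502, shift 0.1502 / 0.919 = 0.163

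Bias in the arm difference:

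| Stopped | ρ = 0.3 | ρ = 0.5 | ρ = 1 (ceiling) |
|---|---|---|---|
| 3 v 1 | 0.030 | 0.050 | 0.099 |
| 2 v 1 | 0.016 | 0.026 | 0.052 |
| 1 v 0 | 0.019 | 0.032 | 0.064 |
| equal | 0 | 0 | 0 |

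The sign reverses if the arms are swapped. A simulation removing exactly these numbers from 37 per arm agrees to within 0.005 SD.

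**5. Scale.** A plain two-sample t test with 37 per arm, at an assumed 80% power and two-sided 5%, detects d = 0.66. The 0.050 SD figure is 0.050 / 0.66 = 0.08 of that.

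**6. A harsher illustration of direction.** Suppose retained patients change by −20% on active and −10% on sham, so the observed difference is −10 points, and stopped patients worsen by 20% to 40%.

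- 10% stopped on active, none on sham. The active mean over all randomised patients is 0.9 × (−20) + 0.1 × 20 = −16, or −14 with 40% worsening. The full difference is −6 to −4.
- The reverse. The sham mean is 0.9 × (−10) + 0.1 × 20 = −7, or −5. The full difference is −13 to −15.

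These inputs have no basis in the documents. They show that the bias can go either way and that its size depends on figures not reported.

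**The case against.** The strongest reply is that the plan may already do what is asked. The sub-heading names treatment. The SAP counts its time points from randomisation, so they exist for every randomised patient. The final treatment can mean the patient's own last session. An early-termination visit would most naturally appear in the schedule of events, which we lack. All of this stands as evidence of ambiguity. A reader might infer that the plan deliberately drops patients who worsen; the documents do not support that. They show a sentence that says so and a heading that points the other way.

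The second reply is size. The CGI-I trigger needs worsening of at least 2 on two consecutive days within one treatment week, in patients on stable medication. Few would be expected to meet it. This also stands, and it is why the point is minor. A reader might take the 75 enrolled and 56 completed in the continuation summary as a measure of the loss. They are not split by arm or reason, and the 75 is not the AH+ sample alone: the same report gives 65 enrolled from the schizophrenia population.

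Third, the remedy involves a choice of estimand. Medication is held constant only during the treatment interval (*Description of subject population*), so AHRS after a stop may reflect a change of drug as well as tDCS. That is a fair caution about interpretation. It does not argue for leaving the values uncollected.

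A reader might also infer that the CGI-S threshold, having no matching entry limit, distorts the comparison. It does not do so by itself, and a threshold that applies at any time can operate before randomisation.

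**Conclusion.** The concern holds in a limited form. Taken literally, the rule removes both primary AHRS values from any patient who meets the CGI-I trigger, and the reason for the loss is worsening. Whether this was intended is unclear, and a provision in the missing schedule cannot be excluded.

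Under the assumptions of about 37 per arm, bivariate normality and a correlation of 0.3 to 0.5, the bias is about 0.03 to 0.05 SD for 3 v 1 stopped and about 0.02 to 0.03 SD for 1 v 0. It is zero with equal rates, and its direction is unknown. The documents do not say how often the rule fired. Severity is minor; the point is worth making because the correction costs little.

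**What to change.** **For the design.** Reword the rule so that it stops tDCS only. Keep consenting patients in the scheduled post-treatment, 1-month and 3-month AHRS visits, and analyse them in their randomised arm. The safety stop is unchanged, and patients remain free to withdraw. The cost is a wording change and a few off-treatment visits at time points already scheduled. The downside is that later AHRS values may reflect medication changes made after the stop, so the result should be read with that in mind.

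**For the completed dataset.** The continuation report says that all interventions are finished and analysis is ongoing, so visits not held cannot be recovered. Report the number of rule-triggered stops by arm, and include any AHRS collected from those patients in their randomised arm. The cost is one by-arm count. If it is zero in both arms, the point is closed.

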Document Date: December 17, 2018

**Statistical analysis:** The prespecified primary behavioral endpoint was percent change across AHRS items after the five-day treatment conducted using a repeated-measures MANCOVA (rmMANCOVA) with group status as a between-subjects factor and time following randomization (one week and one month) and item (7 individual items) included as within-subject factors. In pre-specified analyses, only baseline AHRS score was used as a covariate. However, higher chlorpromazine equivalents (CPZE)  correlated significantly with higher baseline AHRS total ( $r=0.22$ ,  $p=0.04$ ) and PANSS P3 ( $r=0.30$ ,  $p=0.005$ ) scores, justifying its inclusion as an additional covariate for all analysis. Neither baseline AHRS or CPZE differed significantly between groups.

1. Woods SW. Chlorpromazine equivalent doses for the newer atypical antipsychotics. *J Clin Psychiatry* 2003; **64**(6): 663-7.

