(stimulate) or decrease (inhibit) activity in underlying brain regions. It has been reported that applying inhibitory currents over left auditory regions for 20 min per day over 5 consecutive days leads to significant, long-lasting reductions in auditory hallucinations (6). The present study seeks to replicate this finding and will utilize MRI measures of brain activity and metabolism and behavioral assessments to understand the underlying mechanisms.

Specific Aims and Hypotheses

Specific Aims and Hypotheses

The aim of this study is to evaluate the effects on schizophrenia symptoms of tDCS applied with cathodal (inhibitory) electrode over the left temporo-parietal junction and anodal (excitatory) electrode over the left dorsolateral prefrontal cortex.

Our specific hypotheses are:

1. In comparison to sham, active tDCS treatment will decrease the severity of refractory auditory hallucinations in patients with schizophrenia
2. In comparison to sham, active tDCS treatment will decrease the severity of negative schizophrenia symptoms
3. In comparison to sham, active tDCS treatment will normalize auditory function as reflected in stronger prediction error signals in the auditory cortex during the auditory discrimination task and decreased baseline activity in this region.
4. In comparison to sham, active tDCS treatment will normalize auditory function as reflected in reduced cerebral blood flow in auditory cortex and normalized metabolism.
5. Symptom alleviation following active tDCS treatment will be maintained over the course of 3 months

The two control groups (AVH- and healthy controls) will serve as comparison groups for specific AIM 3 and 4 only.

Description of Subject Population

Sample #1

Specify subject population

Schizophrenia patients with auditory hallucinations

Number of completers required to accomplish study aims

60

Projected number of subjects who will be enrolled to obtain required number of completers

75

Age range of subject population

18-55

Sample #2

Specify subject population

Schizophrenia patients without auditory hallucinations

Number of completers required to accomplish study aims

20

Projected number of subjects who will be enrolled to obtain required number of completers

30

Age range of subject population

18-55

Sample #3

Specify subject population

Non-clinical control participants

Number of completers required to accomplish study aims

20

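### Read literally, the SAP's covariate rule leaves PANSS negative symptoms and the pre/post MRI measures unadjusted for their own baselines, although these are collected

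*SAP*

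**What the plan says.** The SAP is one paragraph and defines one analysis: percent change across the AHRS items, by repeated-measures MANCOVA with group, time and item as factors. It then gives its covariate rule: "In pre-specified analyses, only baseline AHRS score was used as a covariate". CPZE is added because it correlated with baseline AHRS total and with PANSS P3, "justifying its inclusion as an additional covariate for all analysis". Baseline balance between arms is reported for AHRS and CPZE only.

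The protocol's Specific Aims and Hypotheses go further than AHRS. Hypothesis 2 is "In comparison to sham, active tDCS treatment will decrease the severity of negative schizophrenia symptoms". Hypotheses 3 and 4 compare active with sham on MRI measures of auditory cortex function, blood flow and metabolism. Hypothesis 5 concerns maintenance of symptom relief to 3 months.

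The baselines exist. Under Study Procedures, Overview, AH+ Sample, AHRS and "the five dimensions of schizophrenia symptoms assessed in the Positive and Negative Syndrome Scale (PANSS) will be assessed at baseline", after the final treatment, and at 1 and 3 months. MRI is done before and after treatment, but is optional for the treated patients. Neither the SAP nor the protocol text available gives a model for any outcome other than AHRS.

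**The concern.** For an AHRS outcome, baseline AHRS is the natural covariate. For PANSS negative symptoms it is a substitute: it measures a different symptom domain and may explain little of the follow-up score. The outcome's own baseline is usually its best single predictor. The SAP's wording does not confine the AHRS rule to the AHRS model. It speaks of analyses in the plural, says only, and extends CPZE to all analysis partly on the strength of a PANSS item.

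Two things are at stake for hypothesis 2. The first is precision: leaving out a strong predictor wastes power in a small trial. The second is chance imbalance. Randomisation makes the estimate unbiased on average, but in any one small trial the arms can differ at baseline, and an analysis that omits the own baseline carries part of that difference into the estimate. The SAP gives no assurance of balance on PANSS negative symptoms.

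**Working it through.** **Text check**

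| Outcome | Own baseline collected? | Covariates under the literal rule | Own baseline adjusted? |
|---|---|---|---|
| AHRS (hypothesis 1; hypothesis 5 where it concerns AHRS) | Yes | AHRS, CPZE | Yes |
| PANSS negative (hypothesis 2) | Yes | AHRS, CPZE | No |
| MRI measures (hypotheses 3 and 4) | Yes, in scanned patients | AHRS, CPZE | No |

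**Illustration of size**

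The available documents give no alpha, effect size, SD or power calculation, so there is no stated figure to reproduce. All inputs below are assumptions except where a source is named.

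- Two-sided alpha 0.05; true effect 0.5 SD of the follow-up score.
- Correlation r between an outcome's baseline and follow-up: 0.3 to 0.8.
- Correlation of baseline AHRS with follow-up PANSS negative: 0.2. CPZE is assumed to add nothing.
- 30 per arm: the protocol's 60 AH+ completers, split equally (no allocation ratio is given).
- 43 per arm: from the SAP's correlations. With t = r√((n−2)/(1−r²)) and n = 86, r = 0.22 gives t = 2.07, two-sided p = 0.042; r = 0.30 gives t = 2.88, p = 0.005. Both agree with the reported 0.04 and 0.005, so if these are two-sided simple correlations in the randomised patients, n is about 86, and 86/2 = 43. The SAP does not say who was included.

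Residual variance, as a fraction of the follow-up variance:

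- AHRS only: 1 − 0.2² = 0.96
- Own baseline: 1 − r²
- Change score: 2(1 − r)

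Power is that of a two-sample t test (noncentral t, 2n − 2 degrees of freedom) at standardised effect 0.5/√(residual variance).

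| | r = 0.3 | 0.5 | 0.6 | 0.7 | 0.8 |
|---|---|---|---|---|---|
| **30 per arm** | | | | | |
| AHRS only | 49% | 49% | 49% | 49% | 49% |
| Own baseline | 51% | 59% | 66% | 76% | 89% |
| Change score | 36% | 48% | 57% | 69% | 85% |
| **43 per arm** | | | | | |
| AHRS only | 65% | 65% | 65% | 65% | 65% |
| Own baseline | 67% | 75% | 82% | 89% | 97% |
| Change score | 49% | 63% | 73% | 84% | 95% |

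For r from 0.5 to 0.8, own-baseline adjustment gains 10 to 40 points over AHRS only at 30 per arm (59 − 49; 89 − 49), and 10 to 32 at 43 per arm. Over a change score it gains 11 falling to 4 points at 30 per arm, and 12 falling to 2 at 43. At r = 0.3 the gain over AHRS only is 2 points.

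**Chance imbalance**

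The SE of the baseline difference in SD units is √(2/n): 0.258 at 30 per arm, 0.216 at 43. The probability of a difference above 0.3 SD in either direction is 2[1 − Φ(0.3/SE)], which is 25% and 16%. At r = 0.7, a 0.3 SD imbalance shifts an unadjusted follow-up comparison by 0.7 × 0.3 = 0.21 SD, and a change-score comparison by (0.7 − 1) × 0.3 = −0.09 SD.

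These figures illustrate hypothesis 2. They do not apply to the MRI outcomes, where the number scanned is not given.

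**The case against.** The strongest objection is one of placement. The covariate sentence follows directly on the AHRS model, the only model the SAP defines. Read there, baseline AHRS is the outcome's own baseline and the choice is sound. A reader might infer that the secondary outcomes were in fact analysed without their own baselines. The documents do not support that. PANSS negative and MRI are not named in the SAP, and the plural and the phrase about all analysis permit the literal reading without establishing it. This part of the objection stands. It does not remove the point, because on the narrow reading hypotheses 2 to 4 have no stated baseline adjustment at all, and the same sentence would repair it.

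A reader might also extend the point to every other measure collected, such as MATRICS, SQLS and tone matching. The hypotheses name none of these, so the point is confined to hypotheses 2 to 4.

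The comparator matters too. The only outcome form in the SAP is percent change. If PANSS negative were handled that way, baseline would enter through the outcome definition. That is not covariate adjustment, but a change score is then the nearer comparison, and against it the gain is only a few points to about 12. This stands, and the contrast with AHRS only should not be quoted alone.

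Finally, under randomisation the omission causes no bias on average; the imbalance figures describe an unlucky trial.

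**Conclusion.** The point holds for hypothesis 2, and for hypotheses 3 and 4 in scanned patients: on its literal wording the covariate rule uses the wrong baseline for these outcomes, and no sentence supplies the right one. The primary AHRS analysis is untouched, as is hypothesis 5 where it concerns AHRS.

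The size is indicative only. It rests on an assumed 0.5 SD effect, assumed correlations, and an arm size between 30 and 43 that the documents do not settle. Against AHRS only the gain is substantial if r is 0.5 or more and negligible at 0.3; against a change score it is modest. This is a correction that should be made to named secondary hypotheses, and it does not threaten the main result.

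**What to change.** Replace the general covariate sentence with a rule by outcome: in the active-versus-sham comparison each outcome is adjusted for its own baseline value, and baseline AHRS is the baseline covariate for AHRS outcomes only. Name PANSS negative symptoms and each pre/post MRI measure (in patients scanned at both times), and state the model and outcome form for each.

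No new data are needed: the cost is a few lines of SAP text and a re-run of the secondary models. There is one real constraint. The protocol's continuation section says that interventions are complete and a manuscript has been submitted, and the SAP already reports observed correlations, so any change now is made with knowledge of the data. The re-run models should be labelled revised or post hoc and reported beside the originals, not presented as the prespecified analysis.
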